6.1.2. Definitions

6.1.2.1. Study Time Intervals

Induction Period

All subjects who were randomized to the study are considered as entering the Induction Period.

The start of the Induction Period is defined as the date of first injection following randomization. For subjects who were randomized but not dosed, the Induction Period starts at the randomization date.

The end of the Induction Period is defined as the date of PASI measurement at Week 16, or the early termination date if subjects discontinued from study prior to or at Week 16, or Day 117, whichever comes first.

Maintenance Period

All subjects who had Week 16 visit with PASI measurement (except the ones discontinued the study at Week 16) are considered to have entered the Maintenance Period.

The start of the Maintenance Period is defined as the same date as end of the Induction Period, which is the date of PASI measurement at Week 16.

The end of the Maintenance Period is defined as the visit date at Week 104, or the date when the subjects received rescue treatment, or the early termination date if subjects discontinued from study prior to or at Week 104, whichever comes first.

Rescue Period

All subjects in PRN groups who received at least 1 dose of rescue treatment are considered to have entered the Rescue Period, and will be included in the Rescue Period analysis population.

The start of the Rescue Period is defined as the date the patient received the first dose of rescue treatment.

The end of the Rescue Period is defined as the visit date at Week 104, or early termination date if subjects discontinued from study prior to or at Week 104, whichever comes first.

Follow-up Period

All subjects who had Visit 29 are considered to have entered the Follow-up Period, and will be included in the Follow-up Period analysis population.

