6.12. Safety Analyses

All safety evaluations will be based upon the Safety Population as defined in Section [6.1.1](#).

Safety and tolerability will be evaluated in terms of adverse events (AEs), treatment-emergent AEs (TEAEs), discontinuations due to AEs, deaths, other SAEs, permanent discontinuations and interruptions of study drug, laboratory analyses including neutrophil counts and immunogenicity, Columbia Suicide Severity Rating Scale (C-SSRS), vital signs, echocardiogram (ECG) findings, and concomitant medications.

The Induction Period safety analyses will summarize each LY3074828 dose regimen (300 mg, 100 mg, and 30 mg) and compare the pooled LY3074828 dose regimens to placebo. Treatment group comparisons will be analyzed using the methods described in Section [6.1.3](#).

For the Maintenance Period, safety will be summarized by treatment (each PRN arm and 300 mg Q8W). No comparisons will be conducted. Only events occurred in the Maintenance Period will be included in this analysis, that is, no events in the Rescue Period will be included. Only a

smaller set of safety analyses (for example, TEAE, serious adverse events (SAE), AE leading to study treatment discontinuation, TE high/low labs, TE high/low vitals) will be needed for the Maintenance Period.

In addition, an overall summary of safety for all LY3074828 exposed subjects, will be provided by presenting all LY3074528 arms pooled including the Induction, Maintenance, and Rescue Periods; Follow-Up Period separately (if there are meaningful number of subjects); and All Periods + Follow-up Period. Only a smaller set of safety analyses (for example, TEAE, SAE, AE leading to study treatment discontinuation, TE high/low labs, TE high/low vitals) will be needed for the overall safety summary.

Safety event occurring on the same day of the end of a period and the start of next period will be counted towards the next period, for example, if a safety event occurred on the date of PASI measurement at Week 16, the event will be allocated to the Maintenance Period.

Change from baseline analyses will use baseline definition provided in Section 6.1.2.

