6.12.2. Adverse Events

Adverse events will be classified based upon the latest version of the Medical Dictionary for Regulatory Activities (MedDRA). AEs will be recorded at every study visit. Conditions starting on or after the date of informed consent will be considered an AE. Preexisting conditions which worsens in severity on or after the date of informed consent will be considered and recorded as an AE on the AE electronic case report form (eCRF) page from the date of worsening onwards.

A treatment-emergent adverse event (TEAE) is defined as an event that first occurred or worsened in severity after baseline as defined in Section 6.1.2. Both the date/time of the event and the date/time of the dose (that is, injection) are considered when determining TEAEs. TEAE will be assigned to the study period to which it's considered treatment-emergent:

- The MedDRA lowest level term (LLT) will be used when classifying AEs as treatment-emergent.
- The maximum severity recorded for each LLT prior to the first dose date/time in the Induction Period will be used as the pretreatment severity for that LLT. If an event during the baseline period has missing severity, and the event persists during the treatment period, then it will be considered as treatment-emergent, regardless of the postbaseline level of severity. Events with a missing severity during the treatment period will be considered treatment-emergent.
- AEs with a particular LLT will be classified as treatment-emergent if they first start on or after the first dose date/time in the treatment period (that is, a patient has no preexisting conditions with that lowest level term), or if the severity is greater than the pretreatment severity for that lowest level term. If a partial AE start date/time is present, the date/time will be compared as far as possible to the treatment start date/time in order to determine whether the event is treatment-emergent or not. If there is any doubt, the event will be flagged as treatment-emergent.

A follow-up emergent adverse event is defined as an event that first occurred or worsened in severity after the date of Visit 29 or early termination visit (ETV):

- The MedDRA LLT will be used when classifying AEs as follow-up emergent.
- For AEs that are ongoing at the date of Visit 29 or ETV, the maximum severity recorded for each LLT on or prior to the date of Visit 29 or ETV will be used as the follow-up baseline severity for that LLT.

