- If a partial AE start date is present, the date will be compared as far as possible to the date of Visit 29 or ETV in order to determine whether the event is follow-up emergent or not. If there is any doubt, the event will be flagged as follow-up emergent, unless the same event was already counted as treatment-emergent during the Induction Period.

Adverse events and TEAEs will be summarized and analyzed for the safety population for the Induction Period. Treatment comparisons between all Induction Period LY3074828 dose regimens (300 mg, 100 mg, 30 mg) combined and placebo will be conducted using Fisher's exact test. Resulting p-values will be used to help identify potential adverse drug reactions. Significant p-values will need to be interpreted with caution due to the fact that multiplicity is not controlled in this study.

Maintenance Period adverse events and TEAEs will be summarized by treatment. Follow-up emergent adverse events and TEAEs during the Rescue Period will be summarized in the All Periods safety analyses.

Additionally,

- An overall summary of AEs including the number and percentage of patients who experienced TEAE, TEAE by maximum severity, death, SAE, discontinuations from the treatment due to an AE, and TEAEs of special interest.
- TEAE by system organ class (SOC) and PT.
- TEAEs related to study treatment by SOC and PT
- TEAE by maximum severity, SOC, and PT.

If a safety event occurred on the same date of the last date of Induction and the first date of the Maintenance Period, the event will be allocated to the Maintenance Period only.

If a safety event occurred on the same date of the last date of Maintenance and the first date of Rescue, compare the event onset time with rescue dose time to allocate the event to the Maintenance Period or Rescue Period accordingly; if either time is missing, the event will be allocated to the Rescue Period only.

If a safety event occurred on the same date of the last date of Maintenance or Rescue and the first date of the Follow-up Period, the event will be allocated to the previous period (Maintenance or Rescue) only.

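### SAP 6.12 and SAP 6.12.2 give conflicting rules for safety events on a period-boundary day; 6.12 should defer to 6.12.2

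*SAP*

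**What the plan says.** SAP Section 6.12, which introduces all the safety analyses, states: "Safety event occurring on the same day of the end of a period and the start of next period will be counted towards the next" (meaning the following period). Its only example is the date of the Week 16 PASI measurement, where the event goes to Maintenance.

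SAP Section 6.12.2 (Adverse Events) then treats the boundaries one by one:

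- Induction to Maintenance: the event goes to Maintenance.
- Maintenance to Rescue: onset time is compared with the time of the rescue dose. If either time is missing, the event goes to Rescue.
- Maintenance or Rescue to Follow-up: when onset falls on the day that closes one and opens the other, "the event will be allocated to the previous period (Maintenance or Rescue) only".

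Three definitions matter for the last boundary. SAP Section 6.1.2.1 says: "The end of the Maintenance Period is defined as the visit date at Week 104", unless rescue or early termination comes first. The same section says: "All subjects who had Visit 29 are considered to have entered the Follow-up Period"; it gives no start date for that period. In Section 6.12.2 a follow-up emergent event is one that "first occurred or worsened in severity after the date of Visit 29 or early termination visit (ETV"), and severity up to and including that date forms the follow-up baseline.

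**The concern.** The two sections use the same term, safety event, and send an event on the Visit 29 date to different periods. The SAP does not say that the more detailed section overrides the general one, so two programmers could build different tables from the same data.

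The day is not an idle one. In the protocol's Schedule of Activities (Section 2), Q8W subjects are dosed at odd-numbered visits and Visit 29 is marked for dosing; the extension protocol determines that dose only for subjects who enter the extension. PRN subjects are also evaluated for a dose at every visit. Reactions on the day of dosing are what the immediate-hypersensitivity summary (Time Period A, SAP 6.12.2.2) counts, and they can also enter the injection-site summary (SAP 6.12.2.3). Both summaries are planned for Induction and Maintenance, so moving a Visit 29 event out of Maintenance takes it out of them.

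A smaller effect concerns exposure. Maintenance exposure in SAP 6.12.1.1 runs through the last Maintenance visit inclusive. Under the 6.12 rule, the Visit 29 day would stay in the person-time while its events left the numerator of any exposure-adjusted rate.

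**Working it through.** The plan gives no figure to reproduce. The check compares the two rules and then traces single events through the definitions.

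**Step 1. The rules at each boundary**

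| Boundary | SAP 6.12 | SAP 6.12.2 | Same result? |
|---|---|---|---|
| Induction / Maintenance (Week 16) | Maintenance | Maintenance | Yes |
| Maintenance / Rescue | Rescue | By onset time against rescue-dose time; Rescue if a time is missing | No, if onset is recorded before the dose |
| Maintenance or Rescue / Follow-up (Visit 29) | Follow-up | Maintenance or Rescue | No |

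**Step 2. Is the Visit 29 day shared?** Maintenance ends on the Week 104 visit date, and so does Rescue for a rescued subject who completes. The Follow-up start date is not stated. That it falls on the same day is implied by the third rule in 6.12.2 and by the entry condition in 6.1.2.1. Subjects who terminate early without Visit 29 do not enter Follow-up under that condition and have no such day.

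**Step 3. Trace an event through each rule.** Take Visit 29 at its nominal Day 728 (protocol Section 2). The event counts in the Maintenance/Rescue table if it is allocated there. It counts as follow-up emergent if it is allocated to Follow-up and its onset day is later than 728.

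| Onset day | 6.12: period | 6.12: times counted | 6.12.2: period | 6.12.2: times counted |
|---|---|---|---|---|
| 727 | Maintenance/Rescue | 1 | Maintenance/Rescue | 1 |
| 728 | Follow-up, but not follow-up emergent | 0 | Maintenance/Rescue | 1 |
| 729 | Follow-up, follow-up emergent | 1 | Follow-up, follow-up emergent | 1 |

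The zero refers to these two counts only. An event that begins on Day 728 and worsens later would become follow-up emergent.

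**Step 4. How many dosing days are affected?** For a fully dosed Q8W subject, the odd visits from Visit 7 to Visit 29 number (29 − 7)/2 + 1 = 12. By weeks, (104 − 16)/8 + 1 = 12. Both rules place Visit 7 in Maintenance. The 6.12.2 rule keeps all 12 dosing days there; the 6.12 rule keeps 12 − 1 = 11. Visit 29 is 1/12 = 8.3% of the dosing days.

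**The case against.** The best reply is that a specific rule normally governs a general one, and that the rest of the SAP fits 6.12.2. Its follow-up emergent definition begins after the Visit 29 date, its follow-up baseline severity includes that date, and the exposure formula in 6.12.1.1 runs Maintenance through its last visit. The only example in 6.12 is Week 16, where the sections agree. Read this way, every event is counted once. This argument is sound, and it shows which rule the edit should keep. It does not remove the conflict, because the 6.12 sentence has no exception and nothing ranks the two sections.

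A reader might infer that Visit 29 events disappear from the safety report. The documents do not support that. The gap arises only if 6.12 is applied at Visit 29 against the explicit rule for that day. Even then, the event is in the by-patient listing of all adverse events (SAP 6.12.2) and probably in the pooled All Periods + Follow-up summary (SAP 6.12). A separate Follow-up summary, planned if numbers are meaningful, is not expressly limited to follow-up emergent events and might also include it.

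The rescue-day difference is also modest. An event before the rescue dose is not a reaction to that dose, and either placement stays within the pooled Induction, Maintenance and Rescue summary. Only the split between periods changes.

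**Conclusion.** The contradiction stands at two boundaries, Maintenance/Rescue and Visit 29. Its consequence is conditional: if the 6.12 rule were used at Visit 29, an event starting that day would leave the Maintenance (or Rescue) adverse-event counts and would not qualify as follow-up emergent. A Maintenance event would also leave the immediate-hypersensitivity and injection-site summaries. Under 6.12.2 the loss is zero.

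A reader might take the 1 in 12 dosing days as a ceiling on the share of same-day reactions lost. It is not one. The documents give no reaction rates by dose. The share would equal 1/12 only if reactions were equally likely at each dose and all 12 doses were given. It would be larger if reactions clustered late, and smaller if they clustered early.

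The result assumes that Follow-up begins on the Visit 29 date, which the SAP implies but does not state. Maintenance safety is descriptive with no between-group comparisons, and no efficacy result is touched. This is a minor inconsistency, worth correcting because it makes period allocation irreproducible.

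**What to change.** Either limit the boundary sentence in SAP 6.12 to the Week 16 boundary, or replace it with a cross-reference saying that the boundary rules in 6.12.2 govern adverse events. In SAP 6.1.2.1, state that for event allocation Follow-up starts on the day after Visit 29. That matches the follow-up emergent definition and leaves no shared day at that boundary.

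Do not extend the adverse-event allocation to laboratory and vital-sign data. Protocol Section 2 schedules assessments before dosing unless otherwise stated, so the Week 16 next-period rule would move pre-dose Week 16 values into Maintenance. SAP 6.12.4 and 6.12.5 analyse those data by visit, mainly for Induction.

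The cost is one SAP sentence and one added definition. No new data or analyses are needed.

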## 2. Schedule of Activities

Induction Dosing Period (Visits 1-7)								
Visit No.	V1	V2	V3	V4	V5	V6	V7	Comments
Week Relative to Study Drug Start	-4	0	2	4	8	12	16	All activities should be completed prior to any study dose administration unless otherwise stated below.
Day with Visit Tolerance Interval	≤28 from V2	0	14 ± 2	28 ± 3	56 ± 5	84 ± 5	112 ± 5	Visit 1 procedures may be conducted over more than 1 day as long as all tasks are completed within the allowable visit tolerance (at least 3 days should be allowed for receipt of laboratory test results).
Informed consent	X							
Demographics	X							
Height	X							
Physical examination & weight	X	X					X	One complete physical examination (excluding pelvic, rectal, and breast examinations) will be performed at screening. All physical examinations throughout the study should include a symptom-directed evaluation as well as examination of heart, lungs, and abdomen and visual examination of all skin areas (including genitalia and breast areas).
Review & confirm inclusion/exclusion criteria	X	X						
Complete medical/surgical history and habits	X							
Concomitant medications	X	X	X	X	X	X	X	
Preexisting conditions	X							
Adverse events	X	X	X	X	X	X	X	

Induction Dosing Period (Visits 1-7)								
Visit No.	V1	V2	V3	V4	V5	V6	V7	Comments
Week Relative to Study Drug Start	-4	0	2	4	8	12	16	All activities should be completed prior to any study dose administration unless otherwise stated below.
Day with Visit Tolerance Interval	≤28 from V2	0	14 ± 2	28 ± 3	56 ± 5	84 ± 5	112 ± 5	Visit 1 procedures may be conducted over more than 1 day as long as all tasks are completed within the allowable visit tolerance (at least 3 days should be allowed for receipt of laboratory test results).
Vital signs (BP and heart rate), body temperature only at V1 and V2, unless clinically indicated	X	X	X	X	X	X	X	Sitting blood pressure and pulse, to be obtained at approximately the same time as ECG measurements or blood sampling. When multiple assessments are scheduled for the same time point, the order of completion should be as follows: ECG, vital signs, and then blood sampling.
Chest radiography for TB screening (required only if not already done within 3 months prior to screening)	X							Chest radiography (Section 9.4.4.1) will be performed at screening unless such radiography has been performed within 3 months before initial screening (provided the radiographs and/or formal report are available for the investigator’s review).

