### 10.3.1.2. General Considerations for Analyses in the Maintenance Period

For maintenance period efficacy analysis, unless otherwise stated, baseline is defined as the last available value before the initial randomization in the induction period which in most cases will be the value recorded at Week 0 (Visit 2).

For maintenance period safety analysis, for subjects

- randomized to placebo in the induction period and for subjects who did not achieve PASI 90, baseline is defined as the last available value before the treatment reassignment in the maintenance period (Week 16, Visit 7)
- who did achieve PASI 90, baseline is defined as the last available value before the initial randomization which in most cases will be the measure recorded at Week 0 (Visit 2)

Change from baseline and 95% confidence interval will be calculated by treatment as the visit value of interest minus the baseline value for continuous variables. The proportion and 95% confidence interval will be reported by treatment for categorical variables.

The Kaplan-Meier product limit method will be used to estimate the survival curves for time-to-event variables; median time to loss of response will be summarized by treatment.

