Rescue Period (Efficacy and Safety)	
All PRN subjects who received at least 1 dose of rescue treatment:
 
 • For subjects who didn't qualify for rescue treatment but get the rescue dose by mistake, they will still be included in the Rescue Period analysis population. • Unless otherwise noted, efficacy, health outcomes and safety endpoints for the Rescue Period will be analyzed on this population.
All Periods Safety	
All subjects who received at least 1 dose of LY3074828 treatment
 
 • Safety analysis will be analyzed for all subjects who were exposed to at least 1 dose of LY3074828 treatment • All LY3074828-exposed subjects will combined in the All Periods safety analysis

Abbreviation: ITT = intent-to-treat; PRN = as needed.

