6.1.2.2. Definition of Study Baseline

For efficacy, health outcomes, and safety analyses, study baseline is defined as the last non-missing assessment (including unscheduled visits) before the first injection, which in most cases will be the measure recorded at Week 0 (Visit 2). For efficacy/health outcome measures, if the patient does not take any injection, the last available value on or prior to randomization date will be used.

For PSS, the weekly average of at least 4 days of the consecutive 7 days prior to the first injection will be the study baseline score.

In cases where baseline measurements are taken on the same day as injection and no times are recorded, it will be assumed that these measurements are taken prior to the injection.

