6.12.1. Extent of Exposure

6.12.1.1. Duration of Exposure

Duration of exposure to study treatment (defined as time since first injection of study treatment in days) will be summarized by treatment group during the Induction Period, the Maintenance Period, and the combined Induction Period, Maintenance Period, and Rescue Period.

Duration of exposure during the Induction Period will be calculated as:

$$(Date\ of\ last\ study\ visit\ in\ the\ Induction\ Period - Date\ of\ first\ injection\ of\ study\ treatment + 1)$$

Duration of exposure during the Maintenance Period will be calculated as:

$$(Date\ of\ last\ study\ visit\ in\ Maintenance\ Period - Date\ of\ last\ study\ visit\ in\ the\ Induction\ Period + 1)$$

Duration of exposure during the Rescue Period will be calculated as:

$$(Date\ of\ last\ study\ visit\ in\ Rescue\ Period - Date\ of\ First\ Rescue\ Treatment + 1)$$

Duration of exposure to LY3074828 for the combined Induction Period, Maintenance Period, and Rescue Period will be calculated as:

$$(Date\ of\ last\ study\ visit\ in\ the\ Maintenance\ Period - Date\ of\ first\ injection\ of\ LY3074828 + 1)$$

for subjects without rescue and

$$(Date\ of\ last\ study\ visit\ in\ the\ Rescue\ Period - Date\ of\ first\ injection\ of\ LY3074828 + 1)$$

for subjects with rescue

For the combined Induction Period, Maintenance Period, and Rescue Period summaries, exposure will be summarized for all LY3074828 dosing regimens pooled.

Descriptive statistics will be provided for patient days of exposure and the frequency of patients falling into the following different exposure ranges (that is, only the exposure ranges that fall within the treatment period will be presented) will be summarized:

- >0, ≥7 days, ≥14 days, ≥30 days, ≥60 days, ≥90 days, ≥120 days, ≥183 days, ≥365 days, ≥548 days.
- >0 to <7 days, ≥7 to <14 days, ≥14 to <30 days, ≥30 to <60 days, ≥60 to <90 days, ≥90 to <120 days, ≥120 to <183 days, ≥183 to <365 days, ≥365 days to <548 days, and ≥548 days.

Additional exposure ranges may be considered if necessary.

A by-patient listing of exposure duration will be provided.

No inferential analysis for comparison between treatment arms will be performed.

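### For placebo subjects who move to LY3074828, the SAP's baseline, pooling and Week 16 same-day rules do not keep placebo-phase safety findings apart from those on drug

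*SAP*

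**What the plan says.** **Same-day rule.** SAP 6.12 states that "if a safety event occurred on the date of PASI measurement at Week 16, the event will be allocated to the Maintenance Period". SAP 6.12.2 repeats this for adverse events and assigns them to Maintenance alone. At the step from Maintenance to Rescue, 6.12.2 instead tells the analyst to "compare the event onset time with rescue dose time to allocate the event to the Maintenance Period or Rescue Period accordingly", with Rescue as the default when a time is missing. At the step into Follow-up, 6.12.2 keeps the event in the earlier period, against the general next-period rule of 6.12.

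**Order of the visit.** Protocol section 2: "All activities should be completed prior to any study dose administration unless otherwise stated below".

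**Baseline.** SAP 6.1.2.2: "study baseline is defined as the last non-missing assessment (including unscheduled visits) before the first injection". SAP 6.12 refers change-from-baseline analyses to that definition. For treatment emergence, SAP 6.12.2 adds: "The maximum severity recorded for each LLT prior to the first dose date/time in the Induction Period will be used as the pretreatment severity". For Maintenance safety in placebo subjects and subjects without PASI 90, protocol 10.3.1.2 says otherwise: "baseline is defined as the last available value before the treatment reassignment in the maintenance period (Week 16, Visit 7".

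**All Periods Safety.** SAP 6.1.1 admits anyone with at least one LY3074828 dose: "All LY3074828-exposed subjects will combined in the All Periods safety analysis". SAP 6.12 describes the summary as LY arms pooled over Induction, Maintenance and Rescue. SAP 6.12.1.1 introduces the exposure formula with "Duration of exposure to LY3074828 for the combined Induction Period, Maintenance Period, and Rescue Period will be calculated as", and the formula runs from the first LY3074828 injection.

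**Groups.** SAP 6.1.1 has four Maintenance safety groups: three PRN groups and one combined 300 mg Q8W group, which takes all continuing placebo subjects. Under SAP 6.1.2.1 the Week 16 PASI date is both the last day of Induction and the first of Maintenance, and subjects who discontinue at Week 16 do not enter Maintenance.

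**The concern.** For a subject randomised to placebo, drug exposure begins at the first LY3074828 injection, not at the first study injection. A table that describes LY3074828 should use that later date for three things: when events begin to count, what they are compared with, and when exposure begins. The SAP uses the later date only for exposure.

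Two outputs are at stake. The All Periods summary is the trial's overall statement on LY3074828 safety, and two programmers working from the same text could fill it differently. The 300 mg Q8W column in Maintenance holds all continuing placebo subjects, so findings that arose before any LY3074828 can appear there. In addition, Induction is the only randomised placebo comparison, and it gives up its last day for continuing subjects but keeps it for those who leave at Week 16.

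**Working it through.** There is no stated figure to reproduce. The check traces the rules and then sizes what can be sized.

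**1. Week 16 allocation.** Take a continuing placebo subject with an event that begins on the day of the Week 16 visit, before the injection.
- It follows the first Induction dose, so it can qualify as treatment-emergent.
- It falls on the PASI date, so it goes to Maintenance only.
- The subject's Maintenance group is 300 mg Q8W, so it is reported there and not under placebo.

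The destination differs for others. Events of LY PASI 90 responders go to their PRN group. Events of LY non-responders move between LY groups. Events of Week 16 discontinuers stay in Induction.

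**2. Baseline.** Take a laboratory value in a placebo subject.
- Normal before placebo, high from Week 8, still high at Week 20: the SAP baseline shows a shift to high on 300 mg Q8W; the protocol's Week 16 baseline shows none.
- High before placebo, normal at Week 16, high at Week 20: the SAP baseline shows no shift; the protocol's does.

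The error can therefore run in either direction.

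**3. All Periods.** The population includes continuing placebo subjects once dosed. The window spans Induction. Pretreatment severity is fixed before the first Induction dose. No sentence excludes placebo-phase events, while exposure leaves placebo time out.

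**4. Size.** Inputs: 200 subjects, 1:1:1:1, so 50 per arm, and a 60% PASI 90 rate on LY3074828 (SAP 5.2); 16 weeks of Induction and treatment to Week 104 (SAP 5.1). No dropout is assumed.
- Maintenance groups: PRN = 150 x 0.60 = 90; 300 mg Q8W = 60 + 50 = 110; placebo-origin share = 50/110 = 45%. With assumed rates of 30%, 45% and 60% by dose: PRN = 67.5, Q8W = 132.5, share = 50/132.5 = 38%.
- Placebo time at issue: 50 x 16 = 800 patient-weeks.
- LY3074828 time to Week 104: 150 x 104 + 50 x 88 = 15,600 + 4,400 = 20,000 patient-weeks. Placebo share of the total: 800/20,800 = 3.8%.
- With everyone at Week 32: 150 x 32 + 50 x 16 = 5,600 patient-weeks; share 800/6,400 = 12.5%.
- Subjects: if 30% to 60% report a TEAE in 16 weeks on placebo (assumption), 50 x 0.30 = 15 to 50 x 0.60 = 30 subjects have a placebo-phase TEAE.
- Net effect on the any-TEAE row, if the same risk recurs independently in each later 16 weeks (assumption; 88/16 = 5.5 intervals): 15 x 0.7^5.5 = 2.1 or 30 x 0.4^5.5 = 0.2 subjects at Week 104. At a Week 32 cut: 15 x 0.7 = 10.5 or 30 x 0.4 = 12 subjects.
- Induction loses 1 of about 113 days (Day 0 to Day 112). How many events carry that date is not given.

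**The case against.** The strongest reply is that the SAP does not say placebo-phase events count as LY3074828 events. A reader might infer that it does, but the text does not go so far. The summary pools LY arms, and placebo Induction is not an LY arm. SAP 6.12.2 assigns each TEAE to a study period, and the exposure clock suggests that placebo time was meant to be left out. This stands: the defect is a missing exclusion, not an express rule.

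A reader might also infer that every Week 16 event goes to 300 mg Q8W. The four groups in SAP 6.1.1 and the discontinuation exception in 6.1.2.1 rule that out.

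A third tempting reading is that incidence rates are inflated by 800/5,600 = 14% at Week 32 or 800/20,000 = 4% at Week 104, or doubled for placebo-origin subjects alone (32 weeks of events over 16 of exposure). SAP 6.12.2.1 and 6.12.3 plan exposure-adjusted rates only conditionally, and only for Induction and Maintenance, so no planned All Periods output carries those figures. SAP 6.17 does not say that All Periods tables are produced at the second interim analysis either.

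On the same-day rule, it is prespecified, applies to all arms and trims about one day. Maintenance is descriptive, and the protocol sentence on visit order governs procedures, not event onset. All true, and no differential bias against placebo is shown. The rule still sends a known pre-dose event to a drug column. SAP 6.12.2 says date and time of event and dose are considered for TEAE status, but does not reconcile this with allocation by date.

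On baseline, protocol 10.3.1 allows analysis changes that are not principal features if the clinical study report describes and justifies them. The SAP (June 2017) also predates both protocol amendments. The amendment (b) change list does not touch 10.3.1.2, and what amendment (a) changed is not shown. The conflict between the documents remains, and the SAP gives no reason for it.

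**Conclusion.** The point holds in three parts. The first two are stated rules; the third is a gap.

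1. Week 16 events of continuing subjects are allocated by date alone, so pre-dose events of placebo-origin subjects are reported under 300 mg Q8W, a group of which they form about 38% to 45% under the response rates shown.
2. Baseline and TEAE pretreatment severity for these subjects precede placebo, in conflict with protocol 10.3.1.2. The same conflict applies to LY subjects without PASI 90.
3. Placebo-phase events are not excluded from All Periods, whose exposure clock excludes placebo time.

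The effect is on subject counts. At most 800 placebo patient-weeks are involved, beside 20,000 on LY3074828 to Week 104, with no dropout. Under the assumptions shown, the any-TEAE row would change by about 2 subjects or fewer at Week 104 and by 10 to 12 at a Week 32 cut. For infrequent terms and serious events there is less overlap with later events on drug, so more of any placebo-phase cases would be net additions. The Week 16-day effect cannot be sized. Nothing here affects the primary efficacy analysis. The text should be corrected because the tables are otherwise not uniquely defined.

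**What to change.** 1. **All Periods Safety (SAP 6.1.1, 6.12, 6.12.2).** For subjects randomised to placebo, start event counting and set baseline at the first LY3074828 injection, matching the formula in 6.12.1.1. State that earlier events are excluded.
2. **Maintenance baseline (SAP 6.1.2.2, 6.12.2).** Reconcile the safety baseline and TEAE pretreatment severity with protocol 10.3.1.2 for placebo subjects and subjects without PASI 90, or state and justify the departure.
3. **Week 16 boundary (SAP 6.12, 6.12.2).** Use the method already set for Rescue: compare onset time with dose time, keep pre-dose events in Induction, and name a default when a time is missing. State how events are allocated in subjects not dosed that day, and whether Visit 7 laboratory and vital-sign values fall under the rule. Align 6.1.2.1, where both periods share the date, and the differing Follow-up rules in 6.12 and 6.12.2.

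The cost is a few sentences and a programming flag, with no new data collection.
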